4.4.3. Discontinuation of the study in the event of objective reached

After having informed the Investigator, the Sponsor may terminate the study before its scheduled term. The IRB/IEC(s) and Competent Authorities will be informed according to local regulations.

4.5. Source data

Source data and source documents of the study centre should be clearly identified in a specific, detailed and signed document before the beginning of the study.

5. STUDY POPULATION AND WITHDRAWAL OF PARTICIPANTS

5.1. Inclusion criteria

Participants are eligible to be enrolled in the study only if all of the following criteria apply:

Demographic characteristics

1. Male or female participant age \geq 18 years old.

General criteria

2. Have a histopathological diagnosis (fresh or banked tumor biopsy sample, preferably collected within the last 3 years) consistent with nonresectable or metastatic cholangiocarcinoma and are not eligible for curative resection, transplantation, or ablative therapies.
3. Have documented IDH1 gene-mutated disease (from a fresh tumor biopsy or the most recent banked tumor tissue available) based on central laboratory testing (R132C/L/G/H/S mutation variants tested).
4. Have an ECOG PS score of 0 or 1.
5. Have an expected survival of \geq 3 months.
6. Have at least one evaluable and measurable lesion as defined by RECIST v1.1. Subjects who have received prior local therapy (including but not limited to embolization, chemoembolization, radiofrequency ablation, or radiation therapy) are eligible provided measurable disease falls outside of the treatment field or within the field and has shown \geq 20% growth in size in the post-treatment assessment.
7. Have documented disease progression following at least 1 and no more than 2 prior systemic regimens for advanced disease (nonresectable or metastatic) with progression on the treatment that was most recently given at a minimum. Subjects must have received at least 1 gemcitabine- or 5-FU -containing regimen for advanced cholangiocarcinoma. Systemic adjuvant chemotherapy will be considered a line of treatment if there is documented disease progression during or within 6 months of completing the therapy.
8. Have recovered from toxicities associated with prior anticancer therapy to baseline unless stabilized under medical management.
9. Have adequate bone marrow function as evidenced by:
 - a. Absolute neutrophil count \geq 1,500/mm³ or $1.5 \times 10^9/L$
 - b. Hemoglobin \geq 8 g/dL
 - c. Platelets \geq 100,000/mm³ or $100 \times 10^9/L$
10. Have adequate hepatic function as evidenced by:
 - a. Serum total bilirubin \leq 2 \times upper limit of normal (ULN) unless considered due to Gilbert's disease
 - b. Aspartate aminotransferase (AST) and alanine aminotransferase (ALT) \leq 5 \times ULN
11. Have adequate renal function as evidenced by:
 - a. Serum creatinine $<$ 1.5 \times ULN
OR
 - b. Creatinine clearance \geq 50 mL/min based on the Cockcroft-Gault glomerular filtration rate (GFR) estimation: $(140 - \text{Age}) \times (\text{weight in kg}) \times (0.85 \text{ if female})/72 \times \text{serum creatinine}$

12. Be able to understand and willing to sign the informed consent form and to comply with scheduled visits, treatment plans, procedures, and laboratory tests, including serial peripheral blood sampling and urine sampling, during the study. A legally authorized representative may consent on behalf of a subject who is otherwise unable to provide informed consent if acceptable to and approved by the site's IRB (Subjects who cannot respond to the EORTC-QLQ-C30, EORTC-QLQ-BIL21, or EQ-5D-5L, are provided in at this time will be permitted to enrol and not complete these HRQOL/health economic outcome instruments, assuming all other eligibility criteria are met).

Sex and Contraceptive/Barrier Requirements

13. Women of childbearing potential (WOCBP) must have a negative serum pregnancy test before the start of therapy. WOCBP are defined as having had onset of their first menstrual period and have not undergone a hysterectomy or bilateral oophorectomy or are not naturally postmenopausal (i.e., have not menstruated at all in the preceding 24 consecutive months without any other medical reasons).
 - a. In case subject is a WOCBP: woman must have been tested negative in a serum pregnancy test before the start of therapy and must use highly effective methods of birth control defined as those alone or in combination that result in a low failure rate (i.e., less than 1% per year) when used consistently and correctly such as implants, combined oral contraceptives, some intra-uterine devices (IUDs), or vasectomized partner from the time of giving informed consent throughout the study, and for 90 days after the last dose of ivosidenib. Women using hormonal contraceptive must also use a barrier method.
 - b. In case subject is a man: man must be either vasectomized or use effective contraception. In this last case, the partner of childbearing potential must use highly effective methods of birth control defined as those alone or in combination that result in a low failure rate (i.e., less than 1% per year) when used consistently and correctly, from the time of giving informed consent throughout the study, and for 90 days after the last dose of ivosidenib.

Informed consent

Obtained prior any study-specific procedure as described in [Section 13.3](#) of the protocol.

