11. Have adequate renal function as evidenced by:
 - a. Serum creatinine $< 1.5 \times$ ULN
 - OR
 - b. Creatinine clearance $\geq 50 \text{ mL/min}$ based on the Cockcroft-Gault glomerular filtration rate (GFR) estimation: $(140 - \text{Age}) \times (\text{weight in kg}) \times (0.85 \text{ if female}) / 72 \times \text{serum creatinine}$
12. Be able to understand and willing to sign the informed consent form and to comply with scheduled visits, treatment plans, procedures, and laboratory tests, including serial peripheral blood sampling and urine sampling, during the study. A legally authorized representative may consent on behalf of a subject who is otherwise unable to provide informed consent if acceptable to and approved by the site's IRB. (Subjects who cannot respond to the EORTC-QLQ-C30, EORTC-QLQ-BIL21, or EQ-5D-5L, are provided in at this time will be permitted to enrol and not complete these HRQOL/health economic outcome instruments, assuming all other eligibility criteria are met)
13. Women of childbearing potential (WOCBP) must have a negative serum pregnancy test before the start of therapy. Women of childbearing potential are defined as having had onset of their first menstrual period and have not undergone a hysterectomy or bilateral oophorectomy or are not naturally postmenopausal (i.e., have not menstruated at all in the preceding 24 consecutive months without any other medical reasons).
 - a. In case subject is a WOCBP: woman must have been tested negative in a serum pregnancy test before the start of therapy and must use highly effective methods of birth control defined as those alone or in combination that result in a low failure rate (i.e., less than 1% per year) when used consistently and correctly such as implants, combined oral contraceptives, some intra-uterine devices (IUDs), or vasectomized partner from the time of giving informed consent throughout the study, and for 90 days after the last dose of ivosidenib. Women using hormonal contraceptive must also use a barrier method.
 - b. In case subject is a man: man must be either vasectomized or use effective contraception. In this last case, the partner of childbearing potential must use highly effective methods of birth control defined as those alone or in combination that result in a low failure rate (i.e., less than 1% per year) when used consistently and correctly, from the time of giving informed consent throughout the study, and for 90 days after the last dose of ivosidenib.

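### The Cockcroft-Gault formula in inclusion criterion 11b lacks brackets around its denominator and a creatinine unit; read literally, it makes clearance rise as renal function worsens

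*Protocol*

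**What the plan says.** Protocol Section 5.1, criterion 11, opens with "Have adequate renal function as evidenced by" and offers two routes joined by OR:

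- **11a:** serum creatinine below 1.5 x ULN.
- **11b:** creatinine clearance of at least "50 mL/min based on the Cockcroft-Gault" estimate, followed by the formula.

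The method is named outright: "based on the Cockcroft-Gault glomerular filtration rate (GFR) estimation". The formula starts with 140 minus age, times weight in kg, and ends (in the text's markup) "0.85 \text{ if female})/72 \times \text{serum creatinine". The synopsis prints the same expression, differing only in spacing: "0.85 \text{ if female}) / 72 \times \text{serum creatinine".

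Neither place brackets 72 together with creatinine. Neither gives a unit for creatinine. The documents also give no value for the ULN.

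**The concern.** A one-line expression of the form A/72 x creatinine, evaluated by the usual left-to-right rule, divides by 72 and then multiplies by creatinine. The estimate then goes up when creatinine goes up. That conflicts with 11a, which treats a high creatinine as inadequate function.

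The OR decides who is affected. A subject with creatinine below 1.5 x ULN enters through 11a whatever 11b gives. Route 11b is decisive only for subjects who fail 11a, and these are the subjects with high creatinine, for whom the literal expression overstates most. Low-creatinine subjects who would fail the literal 11b still enter through 11a, so nothing offsets the permissive error.

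At stake is a safety-related entry rule. If a worksheet or an electronic check were built from the printed line, the rule would pass subjects whom it is meant to stop.

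**Working it through.** The plan reports no worked clearance value, so there is no figure to reproduce. The check evaluates the printed expression under both readings.

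**Inputs from the Protocol (Section 5.1 and synopsis):** the constants 140, 0.85 (women) and 72; weight in kg; the 50 mL/min limit; the 1.5 x ULN limit in 11a; the OR between 11a and 11b.

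**Assumed, because the documents are silent:** creatinine in mg/dL; the ULN (the value needed is shown for each example); the subjects' ages, weights and creatinine values.

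**Formulas.** Let k = (140 - age) x weight x (0.85 if female) / 72.

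- Creatinine as divisor: clearance = k / Scr.
- As printed, left to right: clearance = k x Scr.
- Ratio of printed to divisor: Scr squared.
- The subject fails 11a, and so depends on 11b, if ULN is at most Scr / 1.5.

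**Examples.**

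| Assumed subject | k | Scr (mg/dL) | Fails 11a if ULN is at most (mg/dL) | Divisor (mL/min) | As printed (mL/min) | Ratio |
|---|---|---|---|---|---|---|
| Woman, 65 y, 55 kg | 75 x 55 x 0.85 / 72 = 48.7 | 1.8 | 1.20 | 27.1 | 87.7 | 3.24 |
| Man, 70 y, 60 kg | 70 x 60 / 72 = 58.3 | 2.0 | 1.33 | 29.2 | 116.7 | 4 |
| Man, 60 y, 60 kg | 80 x 60 / 72 = 66.7 | 3.0 | 2.00 | 22.2 | 200.0 | 9 |

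Each is below 50 mL/min with creatinine as divisor and above it as printed.

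**Direction.** For an assumed man of 65 years and 60 kg, k = 75 x 60 / 72 = 62.5.

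| Scr (mg/dL) | Divisor (mL/min) | As printed (mL/min) |
|---|---|---|
| 0.6 | 104.2 | 37.5 |
| 1.0 | 62.5 | 62.5 |
| 1.5 | 41.7 | 93.8 |
| 2.0 | 31.2 | 125.0 |
| 3.0 | 20.8 | 187.5 |

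The divisor reading meets the limit at Scr of at most 62.5 / 50 = 1.25. The literal reading meets it at Scr of at least 50 / 62.5 = 0.80. Evaluated for both sexes at 55 years and 70 kg, 65 years and 60 kg, and 75 years and 50 kg, the cut-off is an upper bound of 0.77 to 1.65 mg/dL for the divisor reading and a lower bound of 0.61 to 1.30 mg/dL for the literal one.

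**Why the error is permissive.** The two readings agree only at 1.0 mg/dL, and above that the printed form is always larger. Subjects who fail 11a have creatinine above 1.0 mg/dL whenever the ULN exceeds 1.0 / 1.5 = 0.67 mg/dL.

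**Unit.** If creatinine is entered in a unit that makes the number c times larger, the divisor result shrinks by a factor c and the printed result grows by c. Brackets alone therefore do not make the formula safe. Safety laboratory tests are run locally at each site (Protocol Section 8.2.4), and SAP Section 5.4.2 plans conversion to international units, so the unit cannot be taken for granted.

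**The case against.** The best defence is that the line is a loosely typed fraction whose meaning is plain. The criterion names Cockcroft-Gault, and 11a fixes the direction. A site using a standard calculator divides by creatinine, and a value such as 200 mL/min at creatinine 3.0 would look wrong to a clinician. This stands as an argument about likelihood. It does not make the printed rule correct.

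A stacked fraction could have been flattened when the PDF was read. This is unlikely: an explicit slash appears in both places, and the stacked fractions in SAP Appendix C came through intact. The typeset page will settle it.

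A reader might go further and infer any of the following, none of which the documents support:

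- **That ineligible subjects have been or will be enrolled.** No document describes an automated clearance derivation built from this line, and none shows a wrong enrolment.
- **That the renal criterion stops almost no one.** This assumes that sites set the named method aside. It also overlooks exclusion 30, under which the investigator can exclude a subject for a laboratory abnormality that raises risk. That backstop is discretionary, but it exists.
- **That anyone below 50 mL/min lies outside the intended population.** The OR means 50 is not a floor. The woman in the first example, at creatinine 1.2, has a clearance of 48.7 / 1.2 = 40.6 mL/min with creatinine as divisor and still enters through 11a if the ULN exceeds 1.2 / 1.5 = 0.8 mg/dL.
- **That the primary efficacy set is contaminated.** A subject wrongly admitted and treated would stay in the ITT, and the per-protocol exclusions in SAP Section 3.1 do not mention renal eligibility. But nothing in the documents links renal function to progression as read by the IRC, and Protocol Section 6.3.4 describes ivosidenib as cleared mainly through CYP3A4 metabolism.

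**Conclusion.** The point holds as a defect in the text of an operative eligibility rule. As printed in both places, 11b lacks the brackets and the unit needed to give one answer. Taken literally, it conflicts with 11a and with the method it names.

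The literal reading overstates clearance by creatinine squared: 3.24-fold at 1.8 mg/dL, 4-fold at 2.0 and 9-fold at 3.0. It affects only subjects who fail 11a, and for them it errs towards admission. These sizes rest on creatinine in mg/dL, on the assumed subjects, and on a ULN low enough for each to fail 11a (at most 1.2 mg/dL for the example at 1.8).

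How often this would matter among about 10 subjects cannot be judged from the documents; it may be never. The case for correcting it is that the rule bears on safety, the error is one-sided and the correction is nearly free.

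**What to change.** In criterion 11b of Section 5.1 and in the synopsis, close the formula with / (72 x serum creatinine), with the brackets, and state the creatinine unit. The examples here assume mg/dL; the sponsor should confirm it. Leave the 50 mL/min limit unchanged.

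Check that any eligibility worksheet or eCRF derivation uses the bracketed form and the stated unit. The synopsis gives September 2023 as the study start, so also recheck the clearance of any subject already admitted through 11b.

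The cost is a pair of brackets and a unit in two places, one programming check, and a review of the few records, if any, that relied on 11b. No extra subjects, visits or procedures are needed.

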5.2. Exclusion criteria

Participants are excluded from the study if any of the following criteria apply:

14. Received a prior IDH inhibitor.
15. Received systemic anticancer therapy or an investigational agent < 2 weeks prior to C1D1 (washout from prior immune based anticancer therapy is 4 weeks). In addition, the first dose of study treatment should not occur before a period \geq 5 half-lives of the investigational agent have elapsed.
16. Received radiotherapy to metastatic sites of disease < 2 weeks prior to Day 1.
17. Underwent hepatic radiation, chemoembolization, and radiofrequency ablation < 4 weeks prior to C1D1.

18. Have known symptomatic brain metastases requiring steroids. Subjects with previously diagnosed brain metastases are eligible if they have completed their treatment and have recovered from the acute effects of radiation therapy or surgery prior to study entry, have discontinued corticosteroid treatment for these metastases for at least 4 weeks and have radiographically stable disease for at least 3 months prior to study entry. Note: up to 10 mg per day of prednisone equivalent will be allowed.
19. Have a history of another primary cancer, with the exception of: a) curatively resected nonmelanoma skin cancer; b) curatively treated cervical carcinoma in situ; or c) other primary solid or liquid tumor with no known active disease present that, in the opinion of the Investigator, will not affect subject outcome in the setting of current cholangiocarcinoma diagnosis.
20. Underwent major surgery within 4 weeks of C1D1 or have not recovered from post-surgery toxicities.
21. Pregnancy, possibility of becoming pregnant during the study and breast-feeding women or woman who plans to restart breast-feeding after the IMP administration/intake. Note: In the case where the Investigator has assessed that the subject may be pregnant as a result of medical interview, etc, the subject will be excluded.
22. Are taking known strong cytochrome P450 (CYP) 3A4 inducers or sensitive CYP3A4 substrate medications with a narrow therapeutic window ([Appendix 6](#)), unless they can be transferred to other medications within \geq 5 half-lives prior to dosing.
23. Have an active infection requiring systemic anti-infective therapy or with an unexplained fever $> 38.5^{\circ}\text{C}$ within 7 days of Day 1 (at the discretion of the Investigator, subjects with tumor fever may be enrolled).
24. Have any known hypersensitivity to any of the components of ivosidenib.
25. Have significant active cardiac disease within 6 months prior to the start of study treatment, including New York Heart Association (NYHA) Class III or IV congestive heart failure ([Appendix 7](#)); myocardial infarction; unstable angina; and/or stroke.
26. Have LVEF $< 40\%$ by ECHO scan (or by other methods according to institutional practice) obtained within 28 days prior to the start of study treatment.
27. Have a heart-rate corrected QT interval (using Fridericia's formula) (QTcF) ([Appendix 8](#)) ≥ 450 msec or other factors that increase the risk of QT prolongation or arrhythmic events (e.g., heart failure, hypokalemia, family history of long QT interval syndrome). Bundle branch block and prolonged QTcF interval are permitted with approval of the Sponsor.
28. Are taking medications that are known to prolong the QT interval ([Appendix 9](#)) unless they can be transferred to other medications within \geq 5 half-lives prior to dosing or unless the medications can be properly monitored during the study. (If equivalent medication is not available, QTcF should be closely monitored.)
29. Have known active hepatitis B (HBV) or hepatitis C (HCV) infections, known positive human immunodeficiency virus (HIV) antibody results, or acquired immunodeficiency syndrome (AIDS)-related illness. Subjects with a sustained viral response to HCV treatment or immunity to prior HBV infection will be permitted. Subjects with chronic HBV that is adequately suppressed per institutional practice will be permitted.
30. Have any other acute or chronic medical or psychiatric condition, including recent (within 12 months of Day 1) or active suicidal ideation or behavior, or a laboratory abnormality that may increase the risk associated with study participation or investigational product administration or may interfere with the interpretation of study results and, in the judgment of the Investigator, would make the subject inappropriate for entry into this study.

31. Have known active inflammatory gastrointestinal disease, chronic diarrhea, previous gastric resection or lap band dysphagia, short-gut syndrome, gastroparesis, or other conditions that limit the ingestion or gastrointestinal absorption of drugs administered orally. Gastroesophageal reflux disease under medical treatment is allowed (assuming no drug interaction potential).
32. Have known medical history of progressive multifocal leukoencephalopathy (PML).

Prior/Concomitant therapy

For prior and forbidden concomitant medication, refer to [Section 6.3](#)

5.3. Retest management during screening period, screen failure and re-screening

A participant who has (a) laboratory result(s) that does not satisfy the entrance criteria may have the test(s) repeated providing that the Investigator judges it relevant according to the participant previous results, or medical history and if s/he considers laboratory abnormalities are likely to be transient. Results of the test(s) repeated should be obtained within the allowed screening period. In this case the participant will not be required to sign another informed consent, and the original participant ID number assigned by the Investigator will be used.

In any case, the last result available for each parameter must be considered for the participant inclusion.

Screen failure is defined as participant who does not fulfil at least one of the inclusion/exclusion criteria during the allowed screening period and consequently cannot participate in the study. In exceptional cases, individuals who do not meet the criteria for participation in this study (screen failure) may be re-screened after agreement of the study medical monitor. If a patient is re-screened, the participant will be required to sign another informed consent, and a new participant identification (ID) number will be assigned by the investigator.

5.4. Additional information recorded at the screening /inclusion visit

Not applicable.

5.5. Participant withdrawal

5.5.1. Withdrawal criteria

Subjects have the right to withdraw from the study at any time for any reason. A subject's discontinuation of study treatment or withdrawal from the study will not jeopardize the relationship with their healthcare providers or affect their future care. This decision must be recorded in writing by the study site.

Premature discontinuation of IMP does not mean that the subject prematurely stops the participation in the study.

Subjects discontinuing study treatment for reasons other than withdrawal of consent from overall study participation will be expected to continue in the study including safety follow-up visits and be contacted for survival follow-up.

Should a subject decide to withdraw, all efforts will be made to complete and report the protocol defined study observations as completely as possible and to determine the reason for withdrawal.

In the event a subject discontinues study treatment or withdraws from the study, the Sponsor must be informed. If there is a medical reason for withdrawal, the subject will remain under the supervision of the Investigator until satisfactory health has returned.

When a subject discontinues study treatment or withdraws from the study, the primary reason for discontinuation or withdrawal must be recorded in the appropriate section of the electronic case report form (eCRF) and all efforts will be made to complete and report final study observations as thoroughly as possible.

Criteria for premature discontinuation of IMP are:

Subjects may discontinue or be discontinued from study treatment at any time. In this situation, a subject without documented progressive disease by the Investigator should be followed for tumor assessments until the development of progressive disease and/or survival.

The reasons for premature study treatment discontinuation are:

- Adverse events, according to the judgment of the Investigator, including no recovery in safety parameters
- Certain adverse events (as described in [Section 8.11.1](#) including instances of Grade 4 QTcF prolongation.
- Disease progression (subjects who are, in the opinion of the Investigator, benefitting from treatment [e.g., slow progression] may be allowed to continue study treatment with approval of the Sponsor)
- Physician decision (for reasons that cannot be included in any of the criteria listed above)
- Pregnancy (for reporting see [Section 8.8](#)),
- Major protocol deviation if it interferes with the study evaluations and/or if it jeopardises participant's safety, e.g., any medical event requiring administration of an unauthorized concomitant treatment
- Withdrawal of consent (only for IMP discontinuation): subjects will be asked if they are willing to continue the safety and disease/survival follow-up.

All AEs should be followed until resolution or for a period of 28 days from the last dose of study treatment, whichever is shorter. If the subject withdrew from treatment because of an AE, every effort must be made to perform protocol-specified safety follow-up procedures.

Information to be collected during the last visit of these participants is given in [Section 5.5.2](#). These follow-up modalities are used to ensure the efficacy and safety evaluation of all participants who received the IMP.

Criteria for premature study discontinuation:

- Withdrawal of consent: Subjects may leave the study at any time for any reason if they wish to do so, without consequence. If a subject withdraws consent from overall study

participation (and not just study treatment), no further evaluations should be performed, and no attempts should be made to collect additional data.

- Death.
- Lost to follow-up.
- Study terminated by Sponsor.

